## Prepare the dose

Your study doctor will tell you how much study drug to take or give.

5. Gather the oral syringe, push the plunger all the way down and insert the tip of the oral syringe fully into the press-in bottle adapter. With the syringe in place, turn the bottle upside down.

6. Slowly pull the plunger of the oral syringe to withdraw the dose of study drug needed. Line up the end of the plunger with the marking for your dose of study drug.

**What to do if you see air bubbles:** If there are air bubbles in the oral syringe, keep the bottle upside down and slowly push the plunger so that all of the liquid flows back into the bottle. Repeat step 6 until air bubbles are gone.

Desired dose →

7. When you have measured the correct amount of study drug, leave the oral syringe in the press-in bottle adapter and turn the bottle right side up.

[figure not shown]

8. Carefully remove the oral syringe from the press-in bottle adapter.

[figure not shown]
[figure not shown]
[figure not shown]

### Take or give study drug

9. Place the tip of the oral syringe against the inside of the cheek and gently push the plunger until all of the study drug in the syringe is taken or given.  
**Do not** forcefully push the plunger.  
**Do not** direct the medicine to the back of the mouth or throat. This may cause choking.

## Clean Up

10. Screw the child-resistant cap back on the press-in bottle tightly by turning the cap to the right (clockwise). Do not remove the press-in bottle adapter. The child-resistant cap will fit over it.
	

11. Fill a cup with warm soapy water and clean the oral syringe by drawing water in and out of the syringe using the plunger.
	

12. Remove the plunger from the barrel of the oral syringe and rinse both parts under tap water. Do not wash the oral syringe in the dishwasher.
	

13. Shake off any extra water from the plunger and oral syringe barrel and allow them to air dry until next use. Make sure the oral syringe is completely dry before the next use. A new dosing syringe should be used every day.
	

### **How do I store study drug?**

Store study drug in its original bottle in an upright position, at room temperature (20°C to 25°C [68°F to 77°F]). Keep the child-resistant cap tightly closed. Save all empty, partially used, and unused bottles of the study drug and return the bottles at your next visit.

**Keep study drug out of the reach of children.**

### **Frequently asked Questions:**

**Q: What if there are air bubbles in the oral syringe?**

[figure not shown]
A: Slowly push the liquid back into the bottle and repeat step 6 until the air bubbles are gone.

**Q: What should I do if the oral syringe is not completely dry before use?**

A: If the oral syringe is not completely dry, use a spare syringe provided by your study doctor.

[figure not shown]
Ganaxolone  
Protocol 1042-TSC-3002  
Protocol Date and Version: 19 Apr 2023; v4.0

Marinus Pharmaceuticals Inc.

[figure not shown]
Ganaxolone  
Protocol 1042-TSC-3002  
Protocol Date and Version: 19 Apr 2023; v4.0

Marinus Pharmaceuticals Inc.

[figure not shown]
Ganaxolone  
Protocol 1042-TSC-3002  
Protocol Date and Version: 19 Apr 2023; v4.0

Marinus Pharmaceuticals Inc.

[figure not shown]
Ganaxolone  
Protocol 1042-TSC-3002  
Protocol Date and Version: 19 Apr 2023; v4.0

Marinus Pharmaceuticals Inc.

[figure not shown]
Ganaxolone  
Protocol 1042-TSC-3002  
Protocol Date and Version: 19 Apr 2023; v4.0

[figure not shown]
Marinus Pharmaceuticals Inc.

Ganaxolone  
Protocol 1042-TSC-3002  
Protocol Date and Version: 19 Apr 2023; v4.0

[figure not shown]
Marinus Pharmaceuticals Inc.

[figure not shown]
Ganaxolone  
Protocol 1042-TSC-3002  
Protocol Date and Version: 19 Apr 2023; v4.0

Marinus Pharmaceuticals Inc.

[figure not shown]
Ganaxolone  
Protocol 1042-TSC-3002  
Protocol Date and Version: 19 Apr 2023; v4.0

Marinus Pharmaceuticals Inc.

[figure not shown]
Ganaxolone  
Protocol 1042-TSC-3002  
Protocol Date and Version: 19 Apr 2023; v4.0

Marinus Pharmaceuticals Inc.

Ganaxolone  
Protocol 1042-TSC-3002  
Protocol Date and Version: 19 Apr 2023; v4.0

Marinus Pharmaceuticals Inc.

## LIST OF ABBREVIATIONS

AE	Adverse event
ASM	Anti-Seizure Medication
BMI	Body Mass Index
CRF	Case Report Form
CGI-CSID	Caregiver Global Impression of Change in Seizure Intensity/Duration
CGI-I	Clinical Global Impression of Improvement
CS	Clinically Significant
DB	Double-blind
ECG	Electrocardiogram
eDiary	Electronic Diary
GNX	Ganaxolone
IP	Investigational Product
ITT	Intent-to-treat
kg	Kilogram
kg/m 	Kilogram per Meter Squared
LAR	Legally authorized representative
MedDRA	Medical Dictionary for Regulatory Activities
mg	Milligram
OLE	Open-Label Extension
NCS	Not Clinically Significant
PT	Preferred Term

SAE	Serious adverse event
SAP	Statistical Analysis Plan
SF-36	Short Form 36
SOC	System Organ Class
TEAE	Treatment-emergent Adverse Event
TLF	Table, Listing and Figure
TSC	Tuberous Sclerosis Complex

## 1. INTRODUCTION

This is a Phase 3, global, open-label extension (OLE) study and all participants will receive treatment with GNX after completing Study 1042-TSC-3001 (in this study participants previously randomized to placebo will be titrated to GNX under double-blind conditions prior to study completion) or Study 1042 TSC 2001. In both parent studies, GNX is to be titrated to a maximum dose of 1800 mg/day and given as an oral suspension (50 mg/mL) with food. Participants will continue the GNX dose determined in Study 1042-TSC-3001 or Study 1042-TSC-2001 in this OLE unless a dose change is clinically indicated. Participants who discontinue the IP should undergo a 2-week taper period, which may be shortened, if necessary, for patient safety. Participants who discontinue the IP before the scheduled completion of the study will have an Early Termination Visit, as per Visit 5 (Week 52), and also return to the site 2 weeks after the end of the taper period to complete the safety follow-up assessments. It is estimated that the maximum duration of participation in this study will be approximately 3 years. The purpose of this Statistical Analysis Plan (SAP) is to define the methodology for analyzing and summarizing the data collected during the conduct of Study 1042-TSC-3002.

## **2. STUDY INFORMATION, OBJECTIVES, AND ENDPOINTS**

### **2.1. Protocol and Case Report Form Version**

This SAP is based on 1042-TSC-3002 Protocol Amendment 3 v4.0 dated 19APR2023 and case report forms (CRFs) v6.0 dated 12Sep2024. Unless superseded by an amendment, this SAP will be effective for all subsequent Protocol amendments and CRF versions.

### **2.2. Study Objectives**

#### **2.2.1. Primary Objective**

The primary objective of the study is: to assess the long-term safety and tolerability of GNX as adjunctive therapy for seizures associated with TSC in children and adults.

#### **2.2.2. Secondary Objectives**

The secondary objectives of the study are:

- For the first year, to determine the percentage of change from baseline in 28-day seizure frequency during open-label treatment.
- For the first year, to assess the change in frequency of countable focal seizures frequency from baseline during open label treatment.
- For the first year, to assess changes in mood, behavior, and quality of life using SF-36.
- To assess overall clinical outcome using CGI-I scores by the clinician and the parent(s)/caregiver(s)/LAR(s).
- To evaluate the changes in seizure intensity and duration using the CGI-CSID.

#### **2.2.3. Exploratory Objectives**

- To evaluate the long-term effects of GNX as add-on therapy to antiepileptic medications.

### **2.3. Study Endpoints**

#### **2.3.1. Primary Endpoint**

The primary endpoints are the following safety endpoints:

- Incidence and severity of AEs, SAEs and withdrawals and dose-reductions due to AEs

- Vital sign measurements including blood pressure, heart rate, respiratory rate, body temperature, height, and body weight
- Physical, neurological, and developmental examination
- 12-lead ECG
- Clinical laboratory tests
- C-SSRS.

### **2.3.2. Secondary Endpoints**

The secondary endpoints are:

- Percentage change from baseline in 28-day seizure frequency during open-label treatment (first year only)
- Number (%) of participants considered treatment responders (first year only)
- CGI-I at the last scheduled study visit
- Change from baseline in the quality-of-life scale SF-36 (first year only)
- Change from baseline in the percentage of seizure-free days during treatment, based on seizure type (first year only)
- Change from baseline of CGI-CSID

Note that original baseline in 28-day seizure frequency in the parent study will be applied. For other assessments, the baseline is considered to be Visit 1, the first visit of the OLE.

### **3. STUDY DESIGN**

#### **3.1. Sample Size Considerations**

Approximately 150 participants will be enrolled, which is a combination of participants who completed Study 1042-TSC-3001 or Study 1042-TSC-2001. The total sample size is not powered for the primary and secondary endpoints.

#### **3.2. Multiplicity**

All endpoints will be assessed descriptively. No multiplicity control methodology will be used.

#### **3.3. Interim Analysis**

No formal interim analysis is planned.

## 4. STATISTICAL METHODOLOGY

### 4.1. General Methodology

Unless otherwise stated, SAS®software (Version 9.4 SAS Institute Inc, Cary, NC) will be used for the generation of all tables, graphs, and statistical analyses. Summary statistics including the number of subjects (n), mean, standard deviation, median, minimum and maximum will be presented for continuous variables. Generally, the minimum and maximum values will be presented to the same decimal precision as the raw values, the mean and median values to one more, and the standard deviation, to two more decimal places than the raw values. For categorical variables, per category, the absolute counts (n) and percentages (%) of subjects with data, and if appropriate, the number of subjects with missing data, will be presented. Percentages will be presented to one decimal place.

For AEs, medical history and concomitant medications reported on a per-subject basis, the denominator for the percentage calculation will be the number of subjects in each treatment group. A subject will be considered at risk if the subject is in the analysis set and in the subgroup of interest.

If a p-value is less than 0.0001 it will be displayed as “< 0.0001”. All p-values larger than 0.0001 will be rounded to 4 decimal places.

The results of the primary and secondary endpoints will be summarized separately. The results will be summarized by the treatment received by participants in the parent study. Participant demographics, characteristics, and medical history at randomization or the start of the parent study will be summarized using descriptive statistics.

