#### **4.1.1 Study Duration for Participation**

It is estimated that the maximum duration of participation in this study will be approximately 3 years.

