## **6.7 Intervention After the End of the Study**

Treatment can continue until the sponsor terminates this study.

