## 7.2 Discontinuation/Withdrawal from the Study

All participants or his/her parent(s)/LAR(s) reserve the right to withdraw from the study at any time, as stated in the informed consent/assent form. The investigator may discontinue participants from the clinical study for any of the following reasons:

- Participant is found to have entered the study in violation of the protocol.
- Participant requires the use of a disallowed concomitant medication.
- Participant's condition changes after entering the clinical investigation so that the participant no longer meets the inclusion criteria or develops any of the exclusion criteria.
- Participant or parent(s)/LAR(s) withdraws consent or assent to participate in the study.
- Participant is noncompliant with the procedures set forth in the protocol.
- Participant experiences an AE/SAE that warrants withdrawal from the study.
- Any laboratory, medical, or clinical finding for which clinical intervention should take precedence over study participation. This includes:
  - Aspartate aminotransferase (AST)/serum glutamic oxaloacetic transaminase (SGOT) or alanine aminotransferase (ALT)/serum glutamic pyruvic transaminase (SGPT)  $> 3 \times$  upper limit of normal (ULN).
  - Total bilirubin levels  $> 1.5 \times$  ULN.
  - Estimated glomerular filtration rate (eGFR)  $< 30$  mL/min.
- It is the investigator's opinion that it is not in the participant's best interest to continue in the study.

Decisions to discontinue the study will be made at each participating site by the investigator. If feasible, the reason for discontinuation should be discussed with the sponsor's medical monitor prior to participant's discontinuation.

At the time of discontinuing from the study, if possible, an Early Termination Visit (Visit 13 [Week 156]) should be conducted as shown in the SOA (Table 1). At this visit, participants will start a 2-week taper and then return to the site 2 weeks later for safety follow-up assessments.

If the participant withdraws consent for disclosure of future information, the sponsor may retain and continue to use any data collected before such a withdrawal of consent.

If a participant withdraws from the study, he/she may request destruction of any samples taken and not tested, and the investigator must document this in the site study records.

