### 4.2. Analysis Sets

For the purposes of analysis, the following analysis sets are defined:

- Intent-to-treat (ITT) Set – Includes all enrolled participants. This set will be used for efficacy analyses.
- Safety Analysis Set – Includes all enrolled participants who receive at least 1 dose of the IP. This set will be used for the safety analyses.

The full analysis set is used to analyze endpoints related to the efficacy objectives and the safety analysis set is used to analyze the endpoints and assessments related to safety.

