### 4.3. Statistical Methods for Primary Safety Analyses

#### 4.3.1. Adverse Events

Adverse events (AEs) are collected from the time of informed consent/assent through the defined follow-up period. AEs are coded using MedDRA dictionary, version 24.0 and are

categorized by system organ class (SOC) and preferred term (PT). A treatment-emergent AE (TEAE) is defined as an AE that starts or worsens on or after the first day of dosing with IP. Detailed by-patient listings of all AEs reported during the study will be provided and will include verbatim and coded terms for each AE.

For the safety Analysis Set, the following tabular summaries will be created:

- An overall summary of TEAEs will present the number and percentage of subjects with at least 1 reported TEAE, study drug related TEAE, serious TEAE, TEAE of Grade 3 or higher, study drug infusion interruption, and death
- TEAEs by system organ class and preferred term
- TEAEs by system organ class, preferred term, and maximum severity
- Study drug related TEAEs by system organ class and preferred term
- TEAEs by decreasing frequency of preferred term
- Moderate or severe TEAEs by system organ class and preferred term
- Moderate or severe study drug related TEAEs by system organ class and preferred term
- TEAEs that led to study drug infusion interruption by system organ class and preferred term
- Serious TEAEs by system organ class and preferred term
- Serious study drug related TEAEs by system organ class and preferred term

For incidence reporting, if a subject reported more than 1 AE that was coded to the same preferred term/system organ class, the subject will be counted only once for that specific preferred term/system organ class. For TEAEs presented by severity, the worst severity for each event during the clinical trial will be presented for each subject. If the severity is missing for a TEAE, then a severity of “Severe” will be assigned. The imputed values for severity assessment will be used for incidence summaries, while the actual values will be used in data listings.

For TEAEs presented by relationship to study drug, the closest relationship to study drug for each event during the clinical trial will be presented for each subject. If the relationship to investigational product is missing for a TEAE, a causality of “Related” will be assigned. The imputed values for relationship assessment will be used for incidence summaries, while the actual values will be presented in data listings.

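### The adverse event tables give only crude percentages, with no onset-interval or exposure-adjusted companion, although follow-up can range from one dose to about 3 years

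*SAP*

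**What the plan says.** The sole primary objective is long-term safety and tolerability (Protocol 3, SAP 2.2.1). Incidence and severity of AEs head the list of primary endpoints (SAP 2.3.1).

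**Denominator.** For AEs, SAP 4.1 states that "the denominator for the percentage calculation will be the number of subjects in each treatment group". It adds: "A subject will be considered at risk if the subject is in the analysis set and in the subgroup of interest". Time under observation plays no part in that definition. Results are shown by parent-study treatment.

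**Population and counting.** The Safety Analysis Set in SAP 4.2 "Includes all enrolled participants who receive at least 1 dose of the IP", so one dose is enough. SAP 4.3.1 begins its list of tables as follows: "An overall summary of TEAEs will present the number and percentage of subjects with at least 1 reported TEAE". The remaining tables break the same kind of count down by class, term, severity, relationship or seriousness. If a subject has several events under one term or class, "the subject will be counted only once for that specific preferred term/system organ class". SAP 4.5 keeps the available data of early withdrawals in the analyses.

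**Length of follow-up.** Protocol 4.1.1: "It is estimated that the maximum duration of participation in this study will be approximately 3 years". Under Protocol 7.2, participants or their representatives "reserve the right to withdraw from the study at any time". Protocol 6.7: "Treatment can continue until the sponsor terminates this study". Protocol 10.1.9.2 lets the sponsor stop the study at any time.

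**Exposure.** SAP 5.7 summarizes days on treatment and total dose, but nothing links these to the AE counts. Protocol 9.2.5 names no exposure-adjusted or interval analysis and leaves the detail to the SAP.

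**The concern.** A percentage of subjects with an event estimates a clear quantity when everyone is watched for about the same time. Here one participant may contribute a single dose and another 3 years, and both add exactly one to the denominator. For an event that can occur at any time on treatment, the percentage then mixes the risk with the length of observation. More drop-out or an early stop lowers it and makes the drug look safer.

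This matters more than usual because SAP 3.2 makes all endpoints descriptive. The estimate is the whole primary result, with no test behind it. The planned tables also cannot show whether risk is concentrated early, persists or emerges late, which is a central question for a long-term study. If follow-up happened to differ between the parent-treatment columns, those columns would differ for that reason alone.

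**Working it through.** The plan has no figure to reproduce: it states no expected AE rate, drop-out rate or power. The check is a text search followed by an illustration on assumed rates.

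**Step 1. Is a time-based AE display planned anywhere?** The tables in SAP 4.3.1, the rules in SAP 4.1, 4.5 and 5.7, and Protocol 9.2.5 were read for one. No person-time denominator, time to first event, or AE table by study year or interval was found.

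**Step 2. Fixed follow-up.** With a constant rate λ per patient-year and everyone followed for T years, crude incidence is 1 − exp(−λT). The rates are assumptions.

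| λ (assumed) | 1 year | 3 years |
|---|---|---|
| 0.05 | 1 − exp(−0.05) = 4.9% | 1 − exp(−0.15) = 13.9% |
| 0.20 | 1 − exp(−0.20) = 18.1% | 1 − exp(−0.60) = 45.1% |
| 0.50 | 1 − exp(−0.50) = 39.3% | 1 − exp(−1.50) = 77.7% |

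**Step 3. Drop-out with a 3-year cap.** Let a proportion d leave each year, independently of the event, so the drop-out hazard is μ = −ln(1 − d). Then:

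- mean follow-up = (1 − exp(−3μ))/μ
- crude incidence = λ/(λ + μ) × (1 − exp(−3(λ + μ)))
- mean time at risk of a first event = (1 − exp(−3(λ + μ)))/(λ + μ)

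With λ = 0.20:

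| d per year | μ | Mean follow-up (years) | Crude incidence | Mean time at risk (years) | First events per patient-year at risk |
|---|---|---|---|---|---|
| 10% | 0.105 | 2.57 | 39.3% | 1.965 | 0.393/1.965 = 0.20 |
| 30% | 0.357 | 1.84 | 29.2% | 1.458 | 0.292/1.458 = 0.20 |
| 50% | 0.693 | 1.26 | 20.9% | 1.043 | 0.209/1.043 = 0.20 |

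The risk is the same in all three rows. The crude percentage nearly halves, while the rate stays at 20 per 100 patient-years.

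**Step 4. The opposite case: early onset.** Assume a hazard of 0.8 per year for the first 3 months and 0.02 per year after that, with no drop-out.

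- Cumulative hazard at 1 year: 0.8 × 0.25 + 0.02 × 0.75 = 0.215. Crude incidence is 1 − exp(−0.215) = 19.3%.
- Cumulative hazard at 3 years: 0.2 + 0.02 × 2.75 = 0.255. Crude incidence is 1 − exp(−0.255) = 22.5%.
- Mean time at risk is 0.836 years at 1 year and 2.417 years at 3 years. The exposure-adjusted rates are 0.1935/0.836 = 23.1 and 0.2251/2.417 = 9.3 per 100 patient-years.

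Here the crude percentage hardly moves and the single rate drops by more than half, although the risk pattern is identical. An interval table would show the pattern in both this case and the one in Step 3.

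**The case against.** The strongest reply is that crude percentages are a conventional descriptive display, the study is single-arm and unpowered, no between-group AE test is planned, and exposure is summarized in its own table. That stands as far as it goes: the crude tables are not an error. It does not answer the gap, because a separate exposure summary does not give time at risk to first event for each term. The table shells are a separate document and might add something, but SAP 4.3.1 sets out its own list and it contains no such table.

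A second reply also stands. The constant-rate model favors an exposure-adjusted rate. Protocol 6.2 names somnolence, sedation and lethargy as the most common dose-related events and discusses them in relation to titration, so many events may start early. Step 4 shows that a single rate can then mislead, which is why the interval table should come first.

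A reader might infer more than the documents support:

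- *That all primary safety results are crude percentages.* Laboratory values and vital signs are summarized by visit, and ECGs as values and changes. Apart from the AE tables, only the any-time C-SSRS summary and the worst-value laboratory shift tables share the dependence on follow-up, in part.
- *That staggered entry shortens follow-up.* Protocol 1.3 and 4.4 schedule every participant to Week 160, and the study ends with the last participant. Entry date matters only if the sponsor stops early.
- *That an exposure-adjusted rate would allow comparison with the pooled ganaxolone data.* The figures in Protocol 2.2.2.2 (742/1168, 33/1168 and 118/2172) are themselves crude, with no person-years.
- *That follow-up will differ between the parent groups.* It could, but the documents give no evidence that it will. Everyone receives ganaxolone here, and former placebo participants are titrated before entry.

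**Conclusion.** The point holds for the AE tables. They report the first-listed primary endpoint only as crude percentages over all subjects in each parent-treatment group, while withdrawal or sponsor termination can make follow-up very unequal. For events that keep accruing, crude incidence falls with shorter observation at unchanged risk.

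The direction follows from the counting rule. The size does not come from the documents. It rests on assumed constant rates of 0.05 to 0.50 per patient-year and drop-out of 10% to 50% per year that is unrelated to the event. Within those assumptions the effect ranges from moderate to large; for early-onset events it is small. It would be tempting to say that AE incidence will reflect time on study as much as risk, but without event and drop-out rates that cannot be established.

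This is a worthwhile, inexpensive addition to the primary safety analysis and not the correction of a wrong one. Confidence is high on what the plan omits and moderate on how much the omission will matter.

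**What to change.** Keep the crude percentages. Add to SAP 4.3.1, by SAP amendment before database lock as SAP 6 provides:

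1. TEAE and serious TEAE incidence by onset interval, for example 26 weeks, with the number at risk in each interval.
2. Exposure-adjusted incidence, defined as subjects with a first event per 100 patient-years at risk with a 95% confidence interval, for TEAEs, serious TEAEs and TEAEs leading to withdrawal, overall and by parent group. State that it is to be read with the interval table, because a single rate can mislead when onset is early.

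Three definitions are needed. First, say when time at risk ends (first event, or a stated point after the last dose). Second, say how events already ongoing at the first dose of the extension are handled. Third, say how partly missing onset dates enter the interval table, since several rules in SAP Table 4 set them to the first dose date and so place them in the first interval. SAP 4.3.1 at present lists no table of TEAEs leading to withdrawal, so that category must be added; Protocol 7.1 already requires such discontinuations to be recorded on the AE page.

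The cost is a few tables built from AE onset and treatment dates that are already collected, with days on treatment derived under SAP 5.7. No new data or design change is needed. The additions do not remove bias if drop-out is itself related to adverse events.
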